9.4 Statistical Analyses

9.4.1 General Approach

Statistical analysis will commence with descriptive statistics for each survey question and plotting of the individual data into scatter plots to understand the data distribution. If any information suggests corrective procedures should be employed, the appropriate transformation or non-parametric test will be used.

Categorical values will be reported using descriptive statistics and frequency of occurrence. Key categorical values will also be converted into a percentage of total responses in order to allow an understanding of the prevalence of the response in the sample. For continuous variables, the means with standard deviations, median and range will be reported.

Qualitative data is only expected as a response to two questions, an open ended safety question and an additional comments question. The responses will be evaluated and categorized. Then the frequency of each category will be provided.

For inferential tests such as t-tests and ANOVAs, a p-value of 0.05 and a confidence interval of 95% will be used for statistical significance. The type of hypothesis will determine whether the specific tests will be one-tailed or two-tailed. Hypothesis seeking to understand whether there is or is not a difference will use a two-tailed test while those seeking a greater than or less than relationship will use a one-tailed test. Correlations among some of the variables will also be examined as appropriate.

Statistical analysis process for each hypothesis has already been described in section 9.1. No baseline analysis is used for cross-sectional studies. No interim analyses are planned for cross-sectional one survey studies.

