4 STUDY DESIGN

4.1 Overall Design

This is a post-market retrospective cross-sectional observational study of people using the Mosie Kit for at-home insemination. The goal of the study is to understand the pregnancy rate resulting from using the Mosie Kit of people with known fertility issues or those wishing to conceive without intercourse due to medical reasons such as vaginismus or being in a LGBTQ relationship desiring a child.

This study uses a convenience sample of people who purchased the Mosie Kit in the past 8 complete months prior to the commencement of the study. The complete known list of people will be invited to participate in the study. For the primary hypothesis 1, all study participants will be treated as one group initially. Subsequently, the study participants may be divided into groups according to their age, the type of relationships (heterosexual or LGBTQ), and/or source of infertility to examine the hypothesis as it relates to these subgroups if sufficient sample size indicates this is appropriate; this analysis corresponds to the tertiary hypothesis.

Primary hypothesis 1: Pregnancy rates using the at-home insemination Mosie Kit to deposit semen near or at the cervix (i.e. intracervical insemination) are equivalent or better than traditional in doctor's office intrauterine insemination.

Given the participants can either be people with fertility issues or people in LGBTQ relationships without known problems conceiving or single women wishing to conceive, another primary hypothesis that will be examined is the difference of pregnancy rates in each of these groups. Specifically, the primary hypothesis related to this is as follows:

Primary Hypothesis 2: Pregnancy rates of LGBTQ people or single women using the Mosie Kit where the female has no know fertility issues will be higher than that of heterosexual people with a known fertility cause or those that are designated as having an unexplained fertility issue.

The secondary hypothesis will examine the use of the Mose Kit and its safety as perceived and reported by the study participants. For these hypotheses the participants will be examined as one group as well as categorized by age group and type of relationship. Specifically, the secondary hypothesis will be as follows:

Secondary Hypothesis 1: The participants perceived the Mosie Kit to be easy to use for its intended purpose.

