Analysis: Descriptive statistics will be used to analyze perceived safety. Qualitative analysis will be used on any comments made related to safety. Rates of vaginal infections will be analyzed using descriptive statistics.

Secondary Hypothesis 5: The majority of participants indicate they have little to no safety concerns related to using the Mosie Kit. Alternative hypothesis is the majority of participants will be very concerned or extremely concerned about the safety of using the Mosie Kit.

Analysis: Descriptive statistics of self-reported level of concern. Additionally, safety measures such as hand washing, disposing of the syringe after use, and reading the instructions will be examined using descriptive statistics.

Tertiary Hypothesis 1: There will be higher pregnancy rates when using the Mosie Kit when the source of infertility is male-based than when it is female-based. The alternative hypothesis is there will be lower pregnancy rates when using the Mosie Kit when the source of infertility is male-based than when it is female-based.

Analysis: In addition to the descriptive statistics a t-test will be run to examine this hypothesis.

Tertiary Hypothesis 2: There is a difference in pregnancy rates of people with known fertility issues depending on the source of their infertility. Specifically, the following sources of infertility will be examined if sufficient data is available.

- o PCOS
- Endometriosis
- Low AMH or low ovarian reserve
- Low sperm count
- Sperm motility issues
- Unexplained infertility
- Erectile dysfunction
- Performance issues or sexual anxiety, or inability to orgasm with partner.

Page 27

- Vaginismus or vulvodynia
- Tilted uterus
- Multiple uterus/cervix
- Loss of a fallopian tube

The alternative hypothesis is that there will be no difference in the fertility rates associated with different sources of infertility.

Analysis: Descriptive statistics, t-test, correlations and multiple ANOVAs will be used to examine this hypothesis.

Tertiary Hypothesis 3: There will be a difference between individuals who perform 2 insemination instances as described in the instructions and those that follow a different schedule or dosage number. The alternate hypothesis is that there will be no difference between the individuals that perform the minimum 2 insemination instances and those that follow difference dosage schedule.

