9.4.2 Sub-Group Analyses

All endpoints (primary, secondary and tertiary) will be analyzed based on age, sex, race.ethnicity, SES, relationship preference, male/femaile infertility issues. Only aggregate

information will be used in the final analysis. No tabulation of individual participant data will be used in reporting findings.

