9.4.3 Exploratory Analyses

Additional exploratory data analysis will be conducted to examine the main characteristics of the data. This analysis will be done using descriptive statistics, scatter plots, and odds ratio. If the exploratory analysis warrants the testing of new hypotheses, t-test or ANOVA may be used for further analysis.

Exploratory modeling will be conducted to examine multiple variables and their relationship to the pregnancy outcome. This will include the source of infertility, age, number of inseminations, number of cycles, lying time, and type of relationship. The model will use correlations and goodness of fit tests in its analysis.

1 0 SUPPORTING DOCUMENTATION AND OPERATIONAL CONSIDERATIONS

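### One unadjusted 0.05 level covers two primary hypotheses, up to 12 infertility sources and hypotheses suggested by the same data, with no testing order or correction

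*Combined protocol and SAP*

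**What the plan says.** Section 9.4.1 (General Approach) sets the level: "For inferential tests such as t-tests and ANOVAs, a p-value of 0.05 and a confidence interval of 95% will be used for statistical significance". It adds that hypotheses "those seeking a greater than or less than relationship will use a one-tailed test", so directional hypotheses are tested one-sided at 0.05. Its only mention of correction concerns the shape of the data: "If any information suggests corrective procedures should be employed, the appropriate transformation or non-parametric test will be used". No section gives a multiplicity adjustment, a testing order or a division of alpha.

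The inferential work that falls under this rule is:

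- **Two primary hypotheses.** After Primary Hypothesis 1, Section 4.1 says "another primary hypothesis that will be examined is the difference of pregnancy rates in each of these groups". Section 9.1 plans an ANOVA for Primary Hypothesis 2. For Primary Hypothesis 1 it plans only a comparison with a 10–20% IUI rate and names no test.
- **Infertility source (Tertiary Hypothesis 2, Section 9.1).** Twelve sources are listed, to be examined where data suffice: "Descriptive statistics, t-test, correlations and multiple ANOVAs will be used to examine this hypothesis".
- **Subgroups (Section 9.4.2).** "All endpoints (primary, secondary and tertiary) will be analyzed based on age, sex, race.ethnicity, SES, relationship preference, male/femaile infertility issues". That is six factors if race and ethnicity count as one.
- **Data-suggested hypotheses (Section 9.4.3).** "If the exploratory analysis warrants the testing of new hypotheses, t-test or ANOVA may be used for further analysis".
- **Other tests in Section 9.1.** These belong to Secondary Hypothesis 3, Tertiary Hypotheses 1, 3, 4 and 5, and the additional correlations and t-tests at the end of the section.

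**The concern.** A 5% error rate per test is not a 5% error rate for the study. With two primaries and no statement of how they combine, success on either could be reported as a primary success. With many source or subgroup comparisons, a significant result may simply be the largest of many chance differences. Where a hypothesis is formed by looking at the data and then tested on them, the p-value takes no account of the selection.

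The consequences are practical. The table in Section 3 says the source analysis will show whether the kit works better for particular sources of infertility. Section 10.1.3 foresees a journal article, use on the sponsor's website and possible marketing use. A chance finding for one diagnosis could therefore reach people who are choosing a method of conception. The sample size in Section 9.2 rests on the precision of one overall proportion and allows nothing for multiple tests.

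**Working it through.** **The plan's own figure.** The documents state no familywise error rate. The precision in Section 9.2 reproduces with half-width = 1.96 × √(0.25/n):

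- n = 500: 1.96 × √(0.25/500) = 4.38% (stated 4.4%)
- n = 384: 1.96 × √(0.25/384) = 5.00% (stated 5%)

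**Two primaries.** Inputs: 0.05 per test (Section 9.4.1) and two hypotheses (Sections 4.1 and 9.1). Assumptions: both nulls true, tests independent, and Primary Hypothesis 1 given a test.

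- Chance of at least one false claim: 1 − 0.95² = 9.75%
- At 0.025 each: 1 − 0.975² = 4.94%

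**Infertility sources.** Twelve sources form 12 × 11/2 = 66 pairs. If the pairs were independent, the chance would be 1 − 0.95⁶⁶ = 96.6%. They are not independent, because pairs share groups, so this figure is too high. I simulated all pairwise pooled t-tests at two-sided 0.05 with equal true rates (20,000 runs per setting). Group sizes, rates, equal group sizes and disjoint membership are my assumptions.

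| Usable sources | Pairs | n = 25, rate 20% | n = 25, rate 30% | n = 40, rate 20% | n = 40, rate 30% |
|---|---|---|---|---|---|
| 12 | 66 | 71% | 70% | 70% | 68% |
| 6 | 15 | 37% | 37% | 35% | 34% |
| 4 | 6 | 21% | 21% | 21% | 19% |

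The number of usable sources drives the result. Group size and pregnancy rate hardly matter.

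**One overall source test.** A single 12-group test, simulated with 500 people and equal rates of 15% or 35%, rejects in 4.9–5.0% of runs. Allowing source comparisons only after that test is significant therefore holds the chance of any false source claim near 5% when no source differs. If all 66 pairs were then compared, Holm's first threshold would be 0.05/66 = 0.00076.

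**Data-suggested hypotheses.** Section 9.4.3 sets no limit on their number, so no error rate can be calculated. The nominal 0.05 does not apply to a hypothesis chosen because the same data pointed to it.

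**The case against.** A good part of the opposing case stands.

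- **Not every planned analysis is a test.** In Section 9.1, Secondary Hypotheses 1, 2, 4 and 5 are descriptive and Primary Hypothesis 1 has no named test. Section 9.4.2 says the endpoints are analyzed by the six factors, not that each is tested.
- **The breakdowns are conditional.** Section 4.1 makes the division into groups depend on sample size, and Section 9.1 makes the source comparisons depend on sufficient data.
- **All-pairs testing is not stated.** The plan names t-tests and several ANOVAs, so 66 pairs is a worst case. Twelve groups of 25–40 would need 300–480 people with a listed source out of about 500. The sample also includes single and LGBTQ users without fertility problems, and some sources are likely to be rare. The survey item on contributing diagnoses appears to allow several answers, so groups may overlap.
- **Much of this is already labelled exploratory.** Section 3 groups infertility source and COVID-19 under tertiary/exploratory objectives, and Section 9.4.3 is headed exploratory.

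A reader might infer that chance findings are close to certain. The documents do not support that, because they never state how many tests will be run. Assuming 8 hypotheses plus 8 × 6 subgroup tests (56 tests), or 2 primaries plus 12 sources plus 12 × 6 subgroup tests (86 tests), independence gives 94.3% and 98.8%. Simulations with correlated endpoints and factors give about 85–97%. If instead the subgroups are descriptive and the sources get one overall test, about eight tests remain: 1 − 0.95⁸ = 33.7%. All these figures assume that every null is true.

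The objection does not remove the gap. The plan commits to none of the narrower readings, and it expressly allows several ANOVAs over sources and tests of data-suggested hypotheses at 0.05.

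**Conclusion.** The concern holds in limited form. The plan states a per-test 0.05 and nothing that controls error across tests. The firm figure is 9.75% for the two primaries, if they are independent and both nulls are true. The source figures (about 68–71%, 34–37% and 19–21% for 12, 6 and 4 usable sources) are worst cases that rest on all-pairs testing and on the assumed group sizes, rates and disjoint groups. The subgroup contribution cannot be sized, because Section 9.4.2 does not say whether those analyses are tests. For hypotheses formed on the same data, the right statement is that the p-value loses its nominal error rate and is not confirmatory. To call it meaningless would go too far. The descriptive estimates are unaffected. Only claims of significance are at risk, so this should be settled before analysis.

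**What to change.** 1. **Section 9.4.1, primaries.** Test each primary hypothesis at 0.025 (familywise 4.94% if independent), or use Holm across the two. This first requires one comparator value and a named test for Primary Hypothesis 1. Section 9.1 now gives a range of 10–20%, and its hypothesis (equivalent or better) does not match its null (not higher). A fixed order is possible, but the two questions are unrelated, and the second would be lost if the first failed.
2. **Section 9.1, Tertiary Hypothesis 2.** Do one overall test across the usable sources, then Holm-adjusted comparisons only if it is significant. State beforehand how many respondents make a source usable and how people with several sources are handled.
3. **All other tests.** Label the remaining secondary and tertiary tests, the additional analyses at the end of Section 9.1, and everything under Sections 9.4.2 and 9.4.3 as exploratory. Report estimates with 95% confidence intervals and make no significance claims.
4. **Section 9.4.3.** Refer hypotheses that arise from exploration to the prospective follow-up study foreseen at the end of Section 2.2.

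**Cost.** Only wording changes, with no new data or recruitment. Each primary loses some power. For example, a one-sided test with 80% power at 0.05 has z = 1.645 + 0.842 = 2.487. At 0.025 this leaves 2.487 − 1.960 = 0.527, or about 70% power. Holm recovers part of that loss. Fewer tertiary and subgroup results could be called significant.

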9.4.2 Sub-Group Analyses

All endpoints (primary, secondary and tertiary) will be analyzed based on age, sex, race.ethnicity, SES, relationship preference, male/femaile infertility issues. Only aggregate

information will be used in the final analysis. No tabulation of individual participant data will be used in reporting findings.

9.4.3 Exploratory Analyses

Additional exploratory data analysis will be conducted to examine the main characteristics of the data. This analysis will be done using descriptive statistics, scatter plots, and odds ratio. If the exploratory analysis warrants the testing of new hypotheses, t-test or ANOVA may be used for further analysis.

Exploratory modeling will be conducted to examine multiple variables and their relationship to the pregnancy outcome. This will include the source of infertility, age, number of inseminations, number of cycles, lying time, and type of relationship. The model will use correlations and goodness of fit tests in its analysis.

1 0 SUPPORTING DOCUMENTATION AND OPERATIONAL CONSIDERATIONS

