3 OBJECTIVES AND ENDPOINTS

OBJECTIVES	ENDPOINTS	JUSTIFICATION FOR ENDPOINTS	PUTATIVE MECHANISMS OF ACTION
Primary			
The primary objective is to understand the outcome of using the at-home intracervical insemination Mosie kit, i.e. pregnancy rate after its use.	The primary endpoints is: Pregnancy Rate after up to 6 cycles. Another primary end point is to understand the rates of pregnancy in people who desire to get pregnant without intercourse (i.e. both single and those in LGBTQ relationships.	The ultimate objective of using the Mosie Kit is to end up pregnant. Thus pregnancy rate is a primary endpoint. Specifically, pregnancy rate in up to 6 (six) cycles will be examined as it is the typical standard timeframe for attempting to get pregnant using IVI or IUI before seeking an alternative method. People who have no known fertility issue who are trying to conceive without intercourse such as those who are in LGBTQ relationships or those who are not in any relationship at all will likely have higher pregnancy rates than those with known fertility issues of female origin. Women in LGBTQ relationships wishing to conceive might also have a higher pregnancy rate than those in heterosexual relationships where infertility might be caused by things like low sperm count, sperm motility issues or erectile dysfunction (ED).	The Mosie Kit is intended to be used to deposit semen at or near the cervix where the sperm will have an increased likelihood of entering the uterus and pairing up with the ovum resulting in a pregnancy. Pregnancy rates increase when sperm reaches the ovum and fertilizes it. In people with no known fertility issues, the Mosie kit deposits the semen where it is able to fertilize the ovum. People without infertility issues who want to get pregnant without sex by using the Mosie Baby are also more likely than people with known fertility issues to get pregnant.

Secondary			

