4.3 Justification for Intervention

This is a retrospective cross-sectional study of existing users of the Mosie Kit. Participants will be recruited via email. Specifically, it is planned that participants will receive up to 5 email invitations to participate in the study, however more emails might be used to recruit sufficient participants.. The email will direct them to the study survey where they will read the consent form and choose to participate in the study. The email will contain a link to the survey. If they elect to participate, they will complete the study survey and submit it online. Participation consists of completing a 10-20 minute survey. This is a one time survey. Since no identifying information will be collected, there will be no possibility of follow up.

There is no intervention. This study merely looks at the past experience of using the Mosie Kit. It is important to know the success rates of pregnancy with at-home insemination kits, and understand the usability and safety as there are individuals and couples using these types of options on a regular basis as a means to get pregnant. For people who suffer from infertility, having this information will help them choose whether ICI is right for them and whether the Mosie Kit should be chosen for this method. Additionally, since age is a factor in pregnancy success and risks increase with age, there is a need to understand the success of at home ICI so recommendations can be made as to whether to use ICI and how long to use it before seeking other methods of conception. This study aims to address some of these issues.

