5.1 Inclusion Criteria

In order to be included in the study, the following inclusion criteria will be used.

Inclusion Criteria:

- Provide implicit consent by filling out and submitting the survey.
- Used a Mosie Kit to conceive during at least one cycle.
- At least 18 years old.
- Has an active email on file (presumed or they would not have received an invitation to participate. This information will not be verified as there is a desire to keep the survey completely anonymous.)

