Appendix A: Online Survey Tool and Consent Form (Google Form)

This section shows what the Google Form will look like to the study participant. These are the questions the participant will be asked.

The first page of the study contains the consent form and the question that confirms the participant's agreement to participate.

There is skip logic for certain sections. For example, if the participant selects one cycle of using Mosie, the information related to cycles 2-6 will be skipped. If the participant selects that she is pregnant the questions related to the pregnancy will be asked, otherwise they will be skipped. If a donor was used, the questions related to producing a sperm sample will be skipped.

Note: Final language and questions might be tweaked or revised at any time to increase clarity.

MOSIE-001 © 2020 Mosie Baby Page 38

[figure not shown]
This is the inclusion/exclusion form.

If Participant selected to not participate in the study, he/she will see this screen next. If the participant said he/she is not 18 or older or has not used Mosie this screen will be displayed.

[figure not shown]

Qualifying participants will continue the survey on this page.

[figure not shown]

[figure not shown]
	ch of these diagnoses or issues do you believe are contributing to your rtility? *
	Not applicable
	PCOS
	Endometriosis
	Low AMH or low ovarian reserve
	Low Sperm count
	Sperm motility issues
	Erectile Dysfunction
	Performance issues or sexual anxiety, or inability to orgasm with partner
	Vaginismus or vulvodynia
	Tilted Uterus
	Multiple uterus/cervix
	Unexplained infertility
	Have only one functioning fallopian tube
П	Other:

[figure not shown]
No other method	is attempted			
Male/Female into	ercourse			
IVI or syringe oth	ner than Mosie			
IUI				
Femara				
Clomid				
IVF				
Cervical Cap				
Other:				
	None	1	2	3 or more
How many pregnancies have you had?	0	0	0	0
pregnancies	0	0	0	0
pregnancies have you had? How many live births have you had? How many pregnancies have you had that were	0	0	0	0
pregnancies have you had? How many live births have you had? How many pregnancies have you had	0	0	0	0

[figure not shown]

[figure not shown]
	0	1	2	3+
24-48 hours prior to ovulation	0	0	0	0
within 24 hours of ovulation	0	0	0	0
24-48 hours after ovulation	0	0	0	0
48+ hours after ovulation	0	0	0	0
Did you use Mosie fo Yes No	or another cy	cle?		

[figure not shown]

[figure not shown]

[figure not shown]

[figure not shown]

Mosie Kit Survey

* Required

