[figure not shown]
How did you or your partner time your ovulation? (Select all that apply.) *
Count days in cycle
Track vaginal or cervical fluids
Tracking changes in the cervix
Use ovulation predictor kit
Use an app to estimate ovulation
Basal Body Temperature
Wearable device
Did not time ovulation
Did using Mosie result in a pregnancy? *
O Yes
O No
Back Next Page 10 of 20

[figure not shown]
Never submit passwords through Google Forms.

 $This \ content \ is \ neither \ created \ nor \ endorsed \ by \ Google. \ \underline{Report \ Abuse} - \underline{Terms \ of \ Service} - \underline{Privacy \ Policy}$

Google Forms

Page 56

[figure not shown]

Safe process

Enjoyable

	Very Easy	Easy	Neutral	Difficult	Very Difficult
To collect the semen/sperm sample in the cup?	0	0	0	0	0
To draw up the semen/sperm in the syringe?	0	0	0	0	0
Insert the Mosie syringe into the vagina up to the handles?	0	0	0	0	0
To deposit the semen/sperm at or near the cervix using the syringe?	0	0	0	0	0
My overall impression on the ease of use	0	0	0	0	0
					Page 12 of 20
submit passwords to	through Google Fo				

MOSIE-001 © 2020 Mosie Baby Page 59

MOSIE-001 © 2020 Mosie Baby

Page 60

Pulled the syringe plunger back and forth to confirm it was functioning.

My partner washed their hands

Use a sperm friendly-lubricant.

Thawed out donor sperm from sperm bank

Prepared all items and have them handy ready to use.

Washed the penis

that	apply)?*
	Lie down in a comfortable position.
	Relax
	Receive oral sex
	Stimulate clitoris
	Use any vibratory or non-vibratory stimulation device intravaginally
	Have an orgasm
	Other:
	erall, how well were you able to use the Mosie syringe to inseminate yourself our partner? * Very Able
	our partner? *
or y O O O	our partner? * Very Able Able Not Very Able
or y 0 0 0 0	Very Able Able Not Very Able Not Able at All Volume at All Volume at All Volume at All Volume at All Able at All Volume at All Able at All Able at All
or y O O O	Very Able Able Not Very Able Not Able at All Volong did you remain laying down after using the Mosie syringe? * Less than 15 minutes

Willelf best descri	ibes your lying position? *	
On my stomach	n	
On my side		
On my back		
On my back wit	th my hips elevated by a pillow	
Other:		
O No		
O		
What type of sam	ple did you use? *	
What type of sam	ople did you use? * rom a sperm bank (frozen)	
What type of sam	rom a sperm bank (frozen)	

0 2000	thank 50%	
O 51%-	70%	
O 71% -	80%	
O 81%-	90%	
O 90%-	95%	
O 96%-	100%	

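### Number of cycles is a predictor of person-level pregnancy in the exploratory model, but it is partly set by the outcome, so its estimate reflects when users stopped, not the effect of further cycles

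*Combined protocol and SAP*

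**What the plan says.** Section 9.4.3 states: "Exploratory modeling will be conducted to examine multiple variables and their relationship to the pregnancy outcome". It then lists the variables, "This will include the source of infertility, age, number of inseminations, number of cycles, lying time, and type of relationship", and gives the method as "The model will use correlations and goodness of fit tests in its analysis".

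The visible part of the survey in Appendix A asks for the outcome once per respondent: "Did using Mosie result in a pregnancy". The cycle count is the number of cycles the respondent reports having used, and the form branches on it: "if the participant selects one cycle of using Mosie, the information related to cycles 2-6 will be skipped". The endpoint in section 3 is "Pregnancy Rate after up to 6 cycles".

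The study population (sections 5 and 6.3) is people who bought the kit 2-8 complete months earlier. No section describes a per-cycle, life-table or time-to-event analysis, or censoring of users who are still trying.

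**The concern.** The inclusion criterion in section 5.1 is "Used a Mosie Kit to conceive during at least one cycle". A user who conceives in cycle 1 would normally report one cycle. A user who keeps failing accumulates cycles until she gives up, reaches cycle 6 or is surveyed. Exposure is then partly a consequence of the result, and a person-level association between the two mixes three things: conception, giving up, and the survey cut-off.

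This matters because section 4.3 wants the study to inform practice, so that "recommendations can be made as to whether to use ICI and how long to use it before seeking other methods of conception". Number of cycles is the variable on which that question turns. Section 9.4.3 also allows exploratory findings to lead to new hypothesis tests, and section 10.1.3 foresees publication and use in marketing materials. A larger sample does not help: it makes a false association more certain.

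**Working it through.** **The plan's own figures.** None is given for this model. The design figures in section 9.2 reproduce: 1.96 × √(0.25/500) = 0.0438 (stated 4.4%) and 1.96 × √(0.25/384) = 0.0500 (stated 5%). They supply the N = 500 used below.

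**Inputs.**
- Chance per cycle, p: 10-15% for ICI (section 2.2). It is held constant over cycles, so the true odds ratio for cycle number is 1.0.
- Cycles available, C: purchase 2-8 months before the survey (section 5), with at most 6 cycles counted.
- Probability d of giving up after a failed cycle: not in the documents; varied here.
- Stopping at conception: inferred from the kit's purpose, not stated.

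**Step 1. Share pregnant among users of k cycles.** The probability of reaching cycle k cancels, which leaves

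share(k) = p·P(C≥k) / { p·P(C≥k) + (1−p)·[P(C=k) + d·P(C>k)] }

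Take p = 0.15. In the staggered rows C is uniform on 2 to 8, capped at 6, so P(C = 2, 3, 4, 5) = 1/7 each and P(C = 6) = 3/7. Example, k = 2, d = 0: 0.15 / (0.15 + 0.85/7) = 0.15/0.2714 = 55%.

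| Pattern | k=1 | 2 | 3 | 4 | 5 | 6 |
|---|---|---|---|---|---|---|
| All could reach 6 cycles, d = 0 | 100% | 100% | 100% | 100% | 100% | 15% |
| Staggered, d = 0 | 100% | 55% | 51% | 47% | 41% | 15% |
| Staggered, d = 0.1 | 64% | 44% | 41% | 39% | 35% | 15% |
| All could reach 6, d = 0.6, 0.3, 0.1, 0.05, 0.05 after cycles 1-5 | 23% | 37% | 64% | 78% | 78% | 15% |

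The chance per cycle is 15% in every cell. The gradients come only from stopping and cut-off. In the last row the gradient rises over the first cycles.

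**Step 2. Odds ratio per extra cycle, person-level logistic model.** Simulated users, p = 0.12, purchase 2-8 months earlier, assumed start lag of 0-1 month and 28-day cycles:

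| Giving up after each failed cycle | Odds ratio per extra cycle |
|---|---|
| 0% | 0.64 |
| 10% | 0.75 |
| 20% | 0.82 |
| 50% | 0.94 |
| Mainly after cycle 1 (60, 30, 10, 5, 5%) | 1.09 |

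**Step 3. What 500 surveys would show.** At p = 0.15 with the staggered pattern of step 1:

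| d | Odds ratio | Correlation | Chance of a false significant negative result (two-sided 0.05) |
|---|---|---|---|
| 0 | 0.55 | −0.45 | 100% |
| 0.1 | 0.71 | −0.26 | 100% |
| 0.3 | 0.85 | −0.09 | 56% |
| 0.5 | 0.92 | −0.03 | 10% |

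**Step 4. Same data, one record per cycle.** The odds ratio for cycle number in a discrete-time model is 1.000 in every scenario of the closed-form calculation.

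**Step 5. Number of inseminations.** With p = 0.12 and no true effect, a total over all cycles analysed without cycle number gives odds ratios of 0.86, 0.90 and 0.93 at 0, 10 and 20% giving up. With number of cycles also in the model, it is about 0.99-1.00. A per-cycle count gives 0.98-1.01.

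**The case against.** **It is exploratory.** No hypothesis in section 9.1 rests on this model, and section 9.4.3 names correlations and goodness of fit, not a logistic regression. That is true and it limits the weight of the point. It does not remove the bias: the correlation in step 3 has the same fault as the odds ratio, and the exploratory label does not make a structural artefact interpretable.

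**The direction is not fixed.** A reader might infer that the model must show longer use lowering the chance of pregnancy. The documents do not support that. They give no stop rates, the bias is small under heavy constant giving up, and it reverses if failed users quit mainly after cycle 1. That last pattern is plausible, since section 2.3.2 describes each kit as supplying two inseminations for one cycle at about $89, so going on may mean buying again. This stands.

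**Inseminations.** A reader might extend the point to number of inseminations. Sections 6.1.2, 6.2 and 9.1 (Tertiary Hypothesis 3) treat it as a count within a cycle, and that count is essentially unbiased in step 5. The problem arises only for a total over cycles analysed without cycle number. Section 9.4.3 does not say which count is meant.

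**Other covariates.** A reader might also suspect that the age and infertility-source estimates are distorted. No calculation shows this; a check with one two-group covariate returned 0.49-0.50 against a true 0.49.

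**The survey is only partly visible.** Stopping at conception is inferred, and an item asking for the cycle of conception may sit on a page not shown. Both limits are carried into the verdict and the fix.

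**Conclusion.** The point holds for number of cycles. As planned, its association with pregnancy is biased, usually downward, and its sign depends on stopping behaviour that the plan does not describe measuring. The true odds ratio in the check is 1.0; the person-level model returns about 0.64 to 0.94 for give-up rates from 0 to 50%, and about 1.09 when quitting is concentrated after cycle 1.

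This rests on users normally stopping at conception, a constant 12% chance per cycle (inside the 10-15% of section 2.2), and assumed give-up rates, start lag and cycle length.

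A reader might take this as a flaw in the primary comparison. It is not: Primary Hypotheses 1 and 2 do not use this model. The change should be made because section 4.3 wants guidance on duration of use and this estimate cannot supply it.

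**What to change.** In section 9.4.3:

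- Remove number of cycles as a person-level predictor.
- Use one record per cycle, with conception in that cycle as the outcome, in a discrete-time model or life table with cycle number as the time axis.
- Use the inseminations in that cycle as exposure, and say so, so that the total is not used by default.
- Keep age, source of infertility and type of relationship as person-level covariates.
- Censor non-pregnant users at their last reported cycle.
- Assign conception to the last reported cycle, unless the survey already asks for the cycle of conception. State that this rule misassigns a user who conceived, lost the pregnancy and resumed.

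The cost is SAP wording and reshaping of data; the survey appears to record insemination timing by cycle already. One small downside: lying time appears to be asked once per person, so it enters as a constant across that user's cycles.
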